5.2.3 INFERENCES INVOLVING MULTIPLE COMPARISON GROUPS

Often investigators are not only interested in whether there are differences among multiple groups, but what pairwise differences are statistically significant. When performing many pairwise comparisons among several groups, one should adjust (or protect) the alpha level of the test to reduce the chance of finding spurious significant differences simply because more tests are performed. The DCC currently uses the methods of Hayter (10) to protect the overall alpha level for multiple comparisons. For three-group designs, the procedure is analogous to the Fisher Least Significant Difference (Isd) rule (10). That is, the test for testing whether all the means are equal is done first (alpha = 0.05), and only if the test is significant are the pairwise comparisons are carried out at the alpha level of 0.05 for each comparison.

5.2.4 REGRESSION MODELS

Multivariate regression models allow one to compare the statistical strength of associations among several risk factors in the presence of markers and co-factors. Power is usually increased when using regression models compared to simple univariate comparisons. For continuous endpoints, inclusion of important independent variables in the regression equation serves to reduce the error variance for all other comparisons. For logistic regression, there is also a bias in estimation of the odds ratio, but the direction of the bias can be positive or negative. Thus, regression models are important because they increase the efficiency of proposed comparisons. However, it is required to ensure that there are sufficient numbers of patients to allow regression analyses to take place. Lung HIV investigators will use the convention of having 10 observations for each planned regressor in a multivariate analysis to ensure that the sample size is adequate for this type of analysis.

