In Section 5.2, two commonly used study size formulas for analyses of continuous and categorical end points are presented. These calculations are based upon the comparison of two groups e.g., comparison of COPD patients to a control/comparison group of patients with other types of lung diseases (e.g., a case-control design), or comparison of patients with a specific lung disease who are in the early stages of the disease to patients with the same disease who are in the terminal stages of the disease. Both of these designs would allow for equal allocation of patients into the two groups, but this is not required. DCC staff will assist the investigators with issues concerning differential allocation versus balanced allocation in the design phase of each Lung HIV study. The DCC also has methods to estimate study size for comparing three or more groups and for estimating regression coefficients, but these types of designs are less frequently used and these formulas are not presented here. All study size estimates and power calculations will account for losses in power due to missing data. Sample size formulas will also account for the possibility that multivariate regression may be used in a study. In this circumstance, it is necessary to ensure that sufficient numbers of patients are present in a study

to allow regression to be reliably carried out. In general, if one adheres to a rule of having 10 observations for every regressor anticipated to be included into a regression equation, the design will have adequate numbers to perform the required analyses.

As stated above, the main difference in performing study size calculations and power calculations for observational studies is the unequal number of subjects that fall into the two comparison groups. We have designated these proportions by "a" and "1-a" in all of the study size formulas presented. The other features common to both of the sample size formulas are the critical values used to determine the alpha level and power of the test. We have designated these values as Z_{α} and Z_{β} respectively. "N" is the total sample size necessary for a study. The size of each comparison group can be obtained by multiplying "N" by "a" for one group and N by "1-a" for the other group. We have presented the formulas for study size calculations, but all of these formulas can be algebraically rearranged to give corresponding power calculations.

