5.2.2 ANALYSIS OF PROPORTIONS

Study size calculations for analyses involving proportions are functions of the overall study size, the proportion of subjects in each of the comparison groups, and the difference between the expected proportion of events in the different groups (9). A study size calculation for a two-

$$N = \frac{(Z_{\alpha}\sqrt{\overline{p}}\overline{q}/a(1-a) + Z_{\beta}\sqrt{p_1q_1/a + p_2q_2/(1-a)})^2}{(p_1 - p_2)^2}$$

group comparison of proportions has the following formula:

In the above equation, p_1 is the probability that someone with the characteristic will have a particular event, p_2 is the probability that someone without the characteristic will have the event, \overline{p} is the weighted average (weighted by a) of p_1 and p_2 , and $\overline{q} = 1 - \overline{p}$. Studies of all 1600 patients can have low values of "a" (e.g., 0.1) and low probabilities of outcomes (e.g., 0.1) and still have adequate power to detect relative risks of 2 (93%). However, if a subgroup analysis of 300 patients is performed (such as might be the case if two groups were being compared that only differed with respect to the timing of disease progression), both "a" and the probability of and outcome would have to be higher (e.g., "a" = 0.3, probability of an outcome = 0.2, power = 0.94 to detect a relative risk of 2).

Below we have presented two figures showing the power to detect specified alternatives of p_1 and p_2 assuming that equal numbers of specimens are used in each group, and the proportion of specimens with an attribute (the control event rate) is low (0.1) or moderate (0.3). In both of these figures, we have assumed that the proportion of case specimens with the attribute (the case event rate) will be higher in the alternative. As can be seen from these figures, small sample sizes will be sufficient to detect large differences between event rates. If smaller differences between the two event rates are postulated in the alternative hypothesis, larger study sizes will be necessary.

Comparison of Two Proportions

Control Event Rate Moderate (0.3)

 $\alpha = 0.05$

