The DCC will develop regression and analysis of variance models that will provide meaningful interpretations of the Lung HIV data. It is anticipated that standard analysis methods would be used for continuous variables and for categorical variables, logistic regression would be used. All regression analyses will be performed using the SAS statistical analysis package. SAS has extensive routines to examine the goodness of fit of each analysis package. For linear regression, tests will be made to determine the goodness of fit by examining the residuals of the analysis using influence analysis and the Hosmer-Lemeshow test (14) will be used to test residuals.

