5.3.5 CONCLUSIONS

A preliminary power analysis has been performed for the Lung HIV project. It has been found that the proposed number of patients (N = approximately 1600) is sufficient to allow for small to moderate effects to be detected with adequate power (at least 80%) when testing at the alpha level of 0.05 (two-sided tests) and for larger effect sizes if subgroup analyses are to be performed.

The Lung HIV project offers a unique opportunity to incorporate variables depicting cellular morphology differences, lung morphology differences, lung tissue biochemical differences and genetic differences of different diseases to show how these variables impact the progression of the various lung diseases. The models presented here are general and robust enough to allow important research to be done in this area.

Longitudinal Studies of HIV-Associated Lung Infections and Complications (Lung HIV)

PROTOCOL CHAPTER 6

TABLE OF CONTENTS

Page

6.	DATA COLLECTION AND MANAGEMENT	6-1
	6.1 Data Collection Forms	6-2
	6.2 Internet Data Management System	6 -3
	6.2.1 Data Entry	6-3
	6.2.2 Study CTMS	6-4
	6.3 Quality Control Procedures	6-5
	6.3.1 Studies and Reports	6-5
	6.3.2 Clinical Center Site Visits	6-6
	6.4 Laboratory Data Management	6-6
	6.4.1 Specimen Tracking	6-6
	6.4.2 On-site Monitoring	6-6
	6.5 DCC Quality Control	6-7

CHAPTER 6: DATA COLLECTION AND MANAGEMENT

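### Sections 5.1 and 5.2.4 treat 10 observations per regressor as adequate for every regression, but for the planned logistic models the count should be of the rarer outcome class

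*Protocol*

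**What the plan says.** Section 5.2.4 sets the sizing convention for adjusted models: "Lung HIV investigators will use the convention of having 10 observations for each planned regressor in a multivariate analysis". Section 5.1 gives the same rule and its warrant: "if one adheres to a rule of having 10 observations for every regressor anticipated to be included into a regression equation", then "the design will have adequate numbers to perform the required analyses". Neither place distinguishes linear from logistic models.

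Logistic models are planned. Section 5.3.3 says that "for categorical variables, logistic regression would be used" and names the SAS procedure for unconditional logistic regression. Table 5.1 lists logistic techniques for CT results and clinical evaluations. Section 5.3.3 also expects interaction terms for effect modifiers.

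On power, Section 5.2.4 says: "Power is usually increased when using regression models compared to simple univariate comparisons". The mechanism it gives, smaller error variance, is stated for continuous end points. For logistic regression it mentions only a bias in the odds ratio that can go either way, and then concludes that regression makes comparisons more efficient.

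Section 5.2.2 gives two worked powers for a relative risk of 2: 93% for N = 1600 (*a* = 0.1, outcome probability 0.1) and 94% for N = 300 (*a* = 0.3, outcome probability 0.2).

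**The concern.** In a linear model every observation informs the coefficients, so a per-observation rule is a usual convention. In a logistic model the information is limited by the smaller of the numbers of events and non-events. A rule that counts all subjects can therefore pass a model with one or two events per regressor. Maximum likelihood at that density pushes odds ratios away from 1 and gives Wald intervals that cover too seldom.

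The rule matters because Chapter 5 frames the review of every Lung HIV proposal. A study could satisfy it exactly and still report exaggerated odds ratios. The power sentence adds to this. Section 5.3.3 says that the groups are not randomized and that adjustment is essential, so the exposure will usually correlate with the covariates. In a logistic model that correlation costs precision, and the printed two-group formulas have no term for it.

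**Working it through.** **1. Reproduce the stated powers.** Inputs are from Section 5.2.2, with two-sided alpha 0.05 from Section 5.3.5. Read the outcome probability as the rate without the characteristic (p2), so p1 = 2 × p2. Rearranging the protocol's formula:

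Zβ = [√N·|p1 − p2| − 1.96·√(p̄q̄/(a(1−a)))] / √(p1q1/a + p2q2/(1−a))

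- N = 1600, a = 0.1, p1 = 0.2, p2 = 0.1: p̄ = 0.1 × 0.2 + 0.9 × 0.1 = 0.11. Zβ = (4.000 − 1.96 × 1.043)/1.304 = 1.50, power 0.933 (stated 93%).
- N = 300, a = 0.3, p1 = 0.4, p2 = 0.2: p̄ = 0.3 × 0.4 + 0.7 × 0.2 = 0.26. Zβ = (3.464 − 1.96 × 0.957)/1.014 = 1.57, power 0.941 (stated 94%).

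Both figures reproduce. Taking the probability as the exposed or the overall rate, or testing one-sided, does not reproduce both. They are unadjusted two-group powers.

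**2. Events per regressor under the rule.** With N/10 regressors, events per regressor = N × rate/(N/10) = 10 × rate: 0.5 at 5%, 1 at 10%, 2 at 20%, 3 at 30% and at most 5 at 50%. Above 50%, non-events are the limit.

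| Example | Events | Regressors allowed | Events each | Regressors at 10 events each |
|---|---|---|---|---|
| N = 300 | 0.26 × 300 = 78 | 30 | 2.6 | 7 |
| N = 1600 | 0.11 × 1600 = 176 | 160 | 1.1 | 17 |

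**3. Effect on the estimates.** Logistic models were simulated with the examples' group sizes and rates. The exposure was binary, the other regressors were pure noise, and fitting was by maximum likelihood (1,000 runs for N = 300, 200 for N = 1600).

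| Example | Regressors | True OR | Median OR | Mean log OR vs truth | 95% CI coverage |
|---|---|---|---|---|---|
| N = 300 | 30 | 2.67 | 3.03 | +14% | 92.4% |
| N = 300 | 7 | 2.67 | 2.72 | +1% | 94.9% |
| N = 1600 | 160 | 2.25 | 2.59 | +19% | 88.5% |
| N = 1600 | 17 | 2.25 | 2.22 | −4% | 95.5% |

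Repeat simulations at the two limits gave inflation of 13 to 16% and 19 to 20%, with coverage of about 90.5 to 92% and 89%. The Monte Carlo standard error of coverage is about √(0.924 × 0.076/1000) = 0.8 points for N = 300 and √(0.885 × 0.115/200) = 2.3 points for N = 1600.

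Under the null, type I error was 7.1% with 30 regressors against 4.2% with 7 (N = 300), and 8.8% with 160 against 7.5% with 17 (N = 1600, 400 runs). The N = 1600 contrast is not resolved by that number of runs, so the point rests on bias and coverage. Rejection rates under the alternative stayed at 92 to 94% throughout, because these covariates were unrelated to the exposure. The damage shown here is to the estimate and interval, not to power.

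**4. Power when confounders correlate with the exposure.** Let R² be the squared multiple correlation of exposure with covariates. The protocol gives none, so the values are assumptions. Approximate effective N = N(1 − R²), put into the formula of step 1:

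| R² | 0 | 0.1 | 0.2 | 0.3 | 0.5 |
|---|---|---|---|---|---|
| N = 1600 | 93% | 91% | 88% | 84% | 73% |
| N = 300 | 94% | 92% | 89% | 84% | 71% |

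The 80% point: N = (1.96 × 1.043 + 0.842 × 1.304)²/0.1² ≈ 987, so R² = 1 − 987/1600 ≈ 0.38. For the subgroup, (1.96 × 0.957 + 0.842 × 1.014)²/0.2² ≈ 186, so R² = 1 − 186/300 ≈ 0.38.

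**The case against.** Several objections carry weight.

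- **The harm sits at the limit.** No analysis in the protocol proposes 30 or 160 regressors. At 15 regressors for N = 300 (5.2 events each) inflation is about 5% with 95% coverage. At 30 regressors for N = 1600 (176/30 = 5.9 each) it is about 1% with 95% coverage. Another run put inflation at 3 to 6% for 5 to 6 events per regressor. This stands. It also shows that 10 events per parameter is a convention, not a boundary of validity.
- **There are other safeguards.** Section 5.1 requires a power calculation for each proposal's primary end point, says that sizing will allow for multivariate regression, and refers to methods for regression coefficients that it does not print. Sections 5.3.2 and 5.3.3 also offer contingency tables, Mantel-Haenszel, McNemar, matching and stratification. This stands in part: the only limit on model size that the protocol prints is still the observation count.
- **The power sentence says usually, and its reason is right for continuous end points.** This stands. The fault is that its conclusion extends to regression in general.

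A reader might also infer a larger bias by pairing N = 300 with a 10% outcome rate: 30 events for 30 regressors. Simulations of that pairing gave inflation from 18 to 32% and coverage from 87 to 94%, depending on whether the exposure is binary or continuous. The protocol does not support that as its case. Section 5.2.2 says that with 300 patients the outcome probability would have to be higher, and its example uses 0.2.

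**Conclusion.** The rule is wrong as written for logistic models, and it is stated twice without exception. In the protocol's own examples it allows about four times (30 against 7) and nine times (160 against 17) as many regressors as 10 events each would. At those limits the log odds ratio is inflated by about 13 to 20% and 95% intervals cover about 89 to 92%. These sizes assume noise covariates, a binary exposure and unpenalized maximum likelihood.

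A reader might go further and conclude that Lung HIV analyses are overfitted or underpowered. The documents do not show either. No regressor count is fixed, so the rule only permits overfitting. The power loss depends on an assumed R², and both examples keep the 80% of Section 5.3.5 until R² reaches about 0.38. For linear models the per-observation convention can stay. Severity: should-fix.

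**What to change.** In Sections 5.1 and 5.2.4:

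1. Keep 10 observations per parameter for linear models. For logistic models, limit candidate parameters, counting dummy and interaction terms, by the smaller of events and non-events. About 10 per parameter will serve if it is labelled a convention. Below that, use penalized (Firth) estimation.
2. Confine the power-gain sentence to prognostic covariates of continuous end points.
3. State in Section 5.2.2 that the 93% and 94% are unadjusted. Where an adjusted logistic analysis with confounders correlated with the exposure is planned, inflate N by 1/(1 − R²) under a stated R². This should not be applied to every two-group N, because for continuous end points the reduction in error variance works in the other direction.

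The cost is a few sentences. Some proposals will carry fewer covariates or state a slightly lower power.

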5.2.5 MISSING DATA AND COMPLIANCE

The DCC will adjust study size requirements using the methods of Lachin (8). Under an assumption that data are missing at random one divides the complete data study size by the estimated proportion of individuals expected to have complete studies to arrive at the final study size estimate.

5.3 DATA ANALYSIS

5.3.1 Overview

Data analyses will be carried out in the Lung HIV study for two main purposes. One is to monitor CC performance and the second is to perform appropriate analyses of all study data with particular emphasis on evaluation of comparisons among participant groups. It is anticipated that recruitment and status reports will be generated on a monthly schedule and monitoring reports providing more detailed information about data quality and performance of the CCs and CLs will be generated on quarterly performance reports that will be presented to the SC, the NHLBI and the DSMB. Analyses of study specific objectives will be performed on an "as needed basis." This will include support, as directed by the NHLBI and the DSMB, for discrete and collaborative studies between the Lung HIV project and other investigators.

5.3.2 ANALYSIS FOR STUDIES

Primary analyses for each study will focus on estimating group differences for the designated primary end point and developing statistical models to determine associations and relationships between dependent variables and risk factors. Particular analysis methods will depend on the type of study being performed and the type of end point and covariates being collected.

Analysis of binary end points will be accomplished using contingency table analysis. Significance of results will be assessed with the Chi-square test uncorrected for continuity. Contingency table analysis will also be used for polychotomous dependent variables. Results for stratified analyses will be summarized using the Mantel Haenzel statistic and odds ratio (12). Results of matched pair designs (e.g. synthetic case control studies) will be analyzed using McNemar's test and the odds ratio derived from that test (13).

For continuous variables, comparisons of groups will be accomplished using Student's t-test or the Wilcoxon rank sum test depending on the distributional properties of the data. Stratified designs will be analyzed using regression methods with the strata represented as randomized blocks for the analysis.

5.3.3 REGRESSION ANALYSES AND ADJUSTMENT

It will be essential to adjust study results for potential confounding factors. Three general approaches are proposed: matching, stratification, and regression analyses. In observational studies the group divisions can lead to different profiles of known risk factors in the groups because the group divisions are not randomized. This creates problems when trying to determine which of the risk factors are responsible for a

particular outcome. Matching and stratification represent a non-parametric way to adjust for potential confounding variables and regression models represent a parametric method. Matching and stratification are used to "adjust out" confounding effects when one is not interested in estimating those effects and regression models are used when one is interested in comparing the effects due to a collection of risk factors.

Both of these techniques are important when performing outcome analyses. Not only do regression models control for potential confounding from markers and cofactors, they can also be used to determine if effect modifiers are present which accelerate or delay cellular and biochemical changes involved in the progression of a lung disease. These effect modifiers are usually included in regression models in the form of interactions.

The DCC uses SAS procedures to perform adjusted analyses. PROC FREQ is used to perform Mantel Haenzel analyses, and PROC GLM to perform regressions and analyses of variance. PROC LOGISTIC is used to perform unconditional logistic regression. The standard output from SAS procedures usually provide: point estimates for the regression coefficients, standard error estimates, and confidence intervals. The results of these analyses can be printed into computer files so that they can be directly inserted in progress reports using PROC REPORT.

In some instances, the procedures in SAS will not suffice since SAS procedures usually do not include methods to incorporate information about missing data, nor do they include complex models specifically designed to relate a biological process with the risk of disease progression. In these circumstances, the DCC uses PROC IML and PROC NLIN to program the required models. Utilization of SAS makes transporting the results to other institutions easy since most institutions have the capability to run SAS programs.

Since there are no plans to follow patients after they are enrolled into the study, it will be necessary to construct disease progression profiles from the individual data points that have been collected. Regression methods will be used to accomplish this aim. As part of the data collection efforts, the Lung HIV investigators will be asked to determine (or estimate) the amount of time that has transpired since the patient first developed the conditions that lead to the disease. It is expected that these estimates will be crude, but it may be possible to at least postulate that the disease is in its early stages, middle stages, or late stages.

If it is possible to actually estimate an "age" at which the disease process was initiated, the time since initiation of the disease is the difference between age of the patient at the time of the visit and the age at which the disease was initially developed. A time measure such as this can be used as a blocking factor in regression analyses, or as an actual regressor.

The identification of such a variable would allow the Lung HIV investigators to compare the cellular and biochemical progression of the different lung diseases in a very meaningful way. Under this scenario, it would be possible to develop disease type by time interactions to compare and contrast the different cellular and biochemical changes that take place between the different lung diseases being studied in the Lung HIV.

If it is only possible to create definitions for early, middle, and late stages, it will be more difficult to compare the disease processes of the different lung diseases since it will not be possible to determine if "early," "middle," and "late" mean the same thing in each disease. In this case, the "timing" variable would either not make sense or would be difficult to interpret when included in interaction analyses. However, the ordinal nature of the determinations would allow meaningful comparisons within a specific disease, and one could track the cellular and biochemical changes that occur within a lung disease type.

The DCC will develop regression and analysis of variance models that will provide meaningful interpretations of the Lung HIV data. It is anticipated that standard analysis methods would be used for continuous variables and for categorical variables, logistic regression would be used. All regression analyses will be performed using the SAS statistical analysis package. SAS has extensive routines to examine the goodness of fit of each analysis package. For linear regression, tests will be made to determine the goodness of fit by examining the residuals of the analysis using influence analysis and the Hosmer-Lemeshow test (14) will be used to test residuals.

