2.1 OVERVIEW

The survival rate of HIV-infected persons continues to improve with the utilization of highly active antiretroviral therapy (HAART) and similar clinical strategies. Hence, it is becoming increasingly important to explore the prevalence and treatment of pulmonary diseases within this population.

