2.2.1 Collaborative Lung HIV Study

The collaborative efforts of these project teams will result in a collection of shared datasets and biological specimens that can be utilized by future investigators as well as those contributing directly to the collection. The Lung HIV study will build on existing studies and facilitate the start-up of new projects to further the understanding of the relationship between pulmonary disease and HIV infection. The result will be greater knowledge of the clinical manifestations of HIV-associated pulmonary complications through multidisciplinary research and collaboration.

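### Section 5.3.3 reads disease progression from time since onset across patients alive at enrolment, which mixes progression with survival and era of onset; the net direction of the bias is unknown

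*Protocol*

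**What the plan says.** Section 5.3.3 starts from a premise about follow-up: "Since there are no plans to follow patients after they are enrolled into the study". The method is then derived from that premise; in the section's words, "it will be necessary to construct disease progression profiles from the individual data points that have been collected". The tool for this is regression. The time axis is the investigators' determination or estimate of "the amount of time that has transpired since the patient first developed the conditions that lead to the disease", and the section concedes: "It is expected that these estimates will be crude". On its use in the model: "A time measure such as this can be used as a blocking factor in regression analyses, or as an actual regressor".

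Two inferences are then offered. If an age at onset can be estimated, disease-by-time interactions are to be used to compare how different lung diseases progress, and the section regards that comparison as highly informative. If only early, middle and late stages are available, the section still holds that "one could track the cellular and biochemical changes that occur within a lung disease type".

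The section states two limits: onset estimates are imprecise, and stages may not mean the same thing in different diseases. It names neither survival to enrolment nor treatment era as a limit. Yet section 2.1 opens with this: "The survival rate of HIV-infected persons continues to improve with the utilization of highly active antiretroviral therapy".

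Other sections do not fit the premise of no follow-up. The questionnaire in 4.2.3 is repeated over time for every subject, 4.2.9 provides a form for missed visits, 4.2.11 provides one for deaths, and 5.3.4 assumes 85% follow-up.

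**The concern.** A patient can enter the profile at a long duration only by living that long after onset. If faster progression raises the risk of death, slow progressors are over-represented at the late end, and the fitted line is flatter than the average course of the disease.

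Onset date is enrolment date minus duration. Among patients enrolled at about the same time, a longer duration therefore means onset under older HIV care. A difference between short and long duration may then reflect the era as much as the passage of time.

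The between-disease comparison is the most exposed. Two diseases with the same true rate of progression but different mortality would show different slopes, and the planned interaction test would read that as a difference in progression. The protocol itself fixes both the method and the inference, so this is more than detail left to an analysis plan.

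**Working it through.** **Is there a stated figure to reproduce?** Not for the progression profile. The power statements in 5.2.2 (93% and 0.94) do reproduce, at 0.933 and 0.941 two-sided, but nothing here depends on them. The protocol gives no mortality, no progression rate, no spread of rates and no size for an era effect. Every input below is an assumption.

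**Do the existing safeguards cover it?**
- Section 3.3 asks for recruitment early in clinical care, which is not early after onset.
- Section 5.1 stratifies sampling so that late specimens do not dominate. That changes the mix of patients but does not bring back those who died before enrolment.
- Section 5.3.3 calls for adjustment for confounders, but duration and onset date are nearly collinear. With duration uniform over 10 years and enrolment uniform over w years, their correlation is −1/√(1 + (w/10)²). That is −0.96 for w = 3 and −0.89 for w = 5 (w assumed).
- Section 5.3.4 offers multiple imputation for data missing on enrolled patients, not for people who never enrolled.

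**Survival selection alone.** Decline per year is b ~ Normal(0.20, SD), with negative values redrawn. Time since onset is T ~ Uniform(0, 10) years. The hazard of death at time t is 0.03·exp(k·b·t), so survival to enrolment has probability exp{−0.03·(exp(kbT) − 1)/(kb)}. Among survivors, b·T is regressed on T. The table gives the survivor slope divided by the full-cohort slope, with 2,000,000 patients per cell:

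| SD of b | k = 0 | k = 0.5 | k = 1.0 | k = 1.5 |
|---|---|---|---|---|
| 0.05 | 1.00 | 0.99 | 0.95 | 0.89 |
| 0.10 | 1.00 | 0.95 | 0.83 | 0.69 |
| 0.15 | 1.00 | 0.90 | 0.71 | 0.54 |

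The flattening is about 1-11%, 5-31% and 10-46% by row. With k = 0 there is none, so it arises wholly from the link between progression and death. At SD 0.10, two diseases with equal true slopes but k = 0.5 and k = 1.5 would give fitted slopes in the ratio 0.686/0.947 = 0.72.

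**Adding an era effect.** In the same model, progression is made 1.25 to 1.5 times as fast in years more than 5 before enrolment, with the hazard following the accumulated decline. Fitted slope over the current-care slope:
- SD 0.10, k = 0.5: 1.04-1.13
- SD 0.05, k = 1.0: 1.04-1.11
- SD 0.10, k = 1.5: 0.71-0.73

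**A second model.** Onset is uniform over 20 years, the mean slope is 1.0 with SD 0.3-0.5, and the hazard is 0.03/year multiplied by exp(log hazard ratio × standardised slope). The era break is at 10 years, with or without doubled hazard in the older years. About 69-75% are alive at enrolment. The current-care slope is 1.00, and the fitted slopes are:
- Death unrelated to slope, no era effect: 1.00.
- Log hazard ratio 0.3-0.7 per SD of slope, no era effect: 0.77-0.95.
- The same, with progression 50% faster in the older era: 0.94-1.17.
- The same, with progression 25% slower in the older era: 0.68-0.84.
- 50% faster in the older era, death unrelated to slope: 1.22-1.24.

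Both models agree that survival selection alone lowers the slope and that the two mechanisms together can move it either way.

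**The case against.** The strongest reply is that 5.3.3 is conditional framework text. Methods are chosen per study (5.3.2), proposals pass through reviewed concept sheets (8.2), and confounder adjustment is called essential. That is fair on detail. But the section commits to between-patient profiles and endorses a progression reading of them, and a later study that followed it would inherit both.

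A second reply is that the premise may be wrong. Sections 4.2.3, 4.2.9, 4.2.11 and 5.3.4 imply visits and follow-up, and the study's title calls it longitudinal. If repeat measurements exist, within-patient change avoids the between-patient time axis. This stands, and it belongs in the fix.

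A third reply is that the sizes are assumed and the worst cases extreme. This also stands. At k = 1.5 the average patient's hazard at year 10 is 0.03·exp(1.5 × 0.2 × 10) = 0.60 per year, and only about 27% of those 8-10 years from onset are alive. The upper ends describe a very lethal disease.

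A reader might also infer that the fastest progressors have in fact died. The protocol gives no rates to show this. Section 4.2.4 lists bacterial pneumonia, PCP and TB beside COPD and PAH, and a ten-year duration axis cannot be assumed for acute infections.

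**Conclusion.** The plan is wrong as written in what it lets investigators conclude. A regression of single measurements on time since onset, among patients alive at enrolment, does not isolate progression, and a disease-by-time interaction from it does not isolate a difference in progression rate.

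A reader might go further and say that the plan understates progression. That holds for survival selection taken alone, and only where faster progression raises mortality. It does not hold for the combined bias: assumed faster progression under older care pushes the fitted slope above the current-care slope in several scenarios. The documents do not settle the net direction.

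The sizes are illustrations under assumed inputs and not estimates for this study. The problem applies mainly to chronic conditions and is smaller to the extent that within-patient data exist. No sample-size or power figure changes.

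**What to change.** In section 5.3.3:

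- **(a)** Reconcile the statement that patients will not be followed with 4.2.3, 4.2.9, 4.2.11 and 5.3.4. Where repeat measurements exist, base progression on within-patient change.
- **(b)** Where they do not, report duration and stage contrasts as cross-sectional differences among surviving patients and not as progression. Do not interpret disease-by-time interactions as differences in progression rate.
- **(c)** As sensitivity analyses only, and where onset dates allow, show the profile restricted to short duration since onset, and by calendar era of onset.

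The restriction in (c) should not become the primary profile. It needs onset dates that the section itself expects to be imprecise, and it would drop the full range of disease that 5.1 asks for. In the first model, limiting to 2 years from onset brings the ratio to 0.99 or higher in every cell, but that assumes onset is known exactly. A stratum for onset before or after a patient's own start of antiretroviral therapy is no substitute for calendar era, and the protocol does not say that this date is collected.

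The cost is a change of wording, a more modest claim and a little more analysis.
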